### **Preexisting Condition**

A preexisting condition is one that is present at the start of the study. A preexisting condition will be recorded as an adverse event if the frequency, intensity, or the character of the condition worsens during the study period.

### **General Physical Examination Findings**

At screening, any clinically significant abnormality will be recorded as a preexisting condition. At the end of the study, any new clinically significant findings/abnormalities that meet the definition of an adverse event will also be recorded and documented as an adverse event.

### **Post-study Adverse Event**

All unresolved adverse events will be followed by the investigator until the events are resolved, the subject is lost to follow-up, or the adverse event is otherwise explained. At the last scheduled visit, the investigator will instruct each subject to report any subsequent event(s) that the subject, or the subject's personal physician, believes might reasonably be related to participation in this study. The investigator will notify the FDA of any death or adverse event occurring at any time after a subject has discontinued or terminated study participation that may reasonably be related to this study. The FDA will also be notified if the investigator should become aware of the development of cancer or of a congenital anomaly in a subsequently conceived offspring of a subject that has participated in this study.

### **Abnormal Laboratory Values**

A clinical laboratory abnormality will be documented as an adverse event if any one of the following conditions is met:

- The laboratory abnormality is not otherwise refuted by a repeat test to confirm the abnormality
- The abnormality suggests a disease and/or organ toxicity
- The abnormality is of a degree that requires active management; e.g. change of dose, discontinuation of the drug, more frequent follow-up assessments, further diagnostic investigation, etc.

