### 6.3.2. Treatment group

**Visit 1/ (= Week 0):** Subjects assigned to treatment groups will receive 500 mg IV rituximab (or start azathioprine or mycophenolate mofetil).

The subject will have a physical exam including BVAS and CDA assessments. We will collect information on concomitant medications and AEs. The subject will be asked to complete a quality of life questionnaire. We will collect 24 ml of blood for research purposes when the subject has blood drawn for routine labs. Women of child-bearing potential will undergo a urine pregnancy test as per indicated clinical care. We will enter the results of routine labs as well as results from B cell analysis in our study database.

**Visits 2 to 13** The subject will have a routine clinical evaluation and a BVAS assessment. We will collect information on adverse events, concomitant medications, and medication compliance. Women of child-bearing potential will undergo a urine pregnancy test as per indicated clinical care. We will enter the results of routine labs in our study database.

Subjects in this treatment groups will receive 500 mg IV rituximab at week 22, week 46, week 70 and week 94 with a +/- 1 week window (or continue azathioprine or mycophenolate mofetil). At those visits, prior to infusion, subjects will have 24 ml of blood drawn for research purposes, including analysis of B cell counts.

The visits will be between every 8 weeks to every 12 weeks, based upon the investigator assessment of how closely an individual subject needs to be followed while on maintenance therapy. The means that the subjects could have between 9 visits (if seen every 12 weeks) and 13 visits (if seen every 8 weeks) until the end of the study.

At week 106, all subjects will undergo a CDA assessment by the nephrologist.

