Time to first positive ANCA test (among those negative at randomization) – The percent who develop a positive ANCA test, and timing to a positive ANCA test will be summarized, with plots of time to this event using Kaplan-Meier curves generated. No statistical analyses for comparisons will be done, but trends and estimates by regimen and by cohort will be used to inform a larger study.

Frequency (number) and severity (by BVAS) of relapse – Among those who relapse, we will evaluate which organs are impacted by disease relapse (using BVAS subsections) and the severity of the relapse

(summarized by the BVAS score). This will be done by regimen and by cohort. Zero in any organ sub-section shows no disease activity in that organ. The total score range for a BVAS is 0 to 64. No statistical analyses are planned, but this will provide information for potential patterns of relapse in specific organs as well as information on the severity of relapses by group.

Occurrence of any infection – all infections will be counted and described by regimen and by cohort.

Frequency/severity/etiology of infections – recurrent infections, severity of infections, with those requiring hospitalization and/or intravenous antibiotics deemed as serious—with etiology of each infection listed. Etiologies will be listed as reported and may include a combination of location (urinary tract, upper respiratory, lung) and type of pathogen (bacterial, viral, fungal or parasitic). All infection metrics (recurrent, severity and type) be described and tallied within each regimen and cohort, but no statistical comparisons will be done. This information is necessary to understand the expected infectious adverse events that can be expected in a larger study.

Frequency and severity of any adverse advent (AEs and SAEs) – These will be catalogued as above for infections – including type of event, relation to therapy/discontinuation of therapy, and outcome of adverse event.

Time to B-cell normalization (that is, % IL-10 Secreting > 45% or % CD5+ B Cells Response > 43%) – the number who normalize will be evaluated; time to normalization will be observed in Kaplan-Meier plots by each regimen and cohort, but no statistical tests will be done to compare groups. These measures will guide the optimal times for follow-up and monitoring in a larger study.

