## Adverse Event

An **adverse event** (AE) is any symptom, sign, illness or experience that develops or worsens in severity during the course of the study. Intercurrent illnesses or injuries should be regarded as adverse events. Abnormal results of diagnostic procedures are considered to be adverse events if the abnormality:

- results in study withdrawal
- is associated with a serious adverse event
- is associated with clinical signs or symptoms
- leads to additional treatment or to further diagnostic tests
- is considered by the investigator to be of clinical significance

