## **8.3 Reporting of Serious Adverse Events and Unanticipated Problems**

All adverse events will be reviewed and recorded in “real time” and reviewed systematically every month by the PI. Adverse events are defined as any untoward or unfavorable medical occurrence in a human subject, including any abnormal sign, symptom, disease, or abnormal laboratory finding temporally associated with the subject’s participation in the research, whether or not considered related to the subject’s participation in the research.

Serious Adverse Events (SAE) will be reported immediately within 1 business days to the UNC IRB, and within 5 business days to the FDA according to the requirements of the IND. Reporting will be done electronically to the UNC IRB (as per current standard operating procedure) and by Fax to both institutions.

For reportable deaths, the initial submission to the UNC IRB may be made by contacting the IRB Director or Associate Director. The AE/Unanticipated Problem Form is required as a follow up to the initial submission.

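### Section 8.1 makes an unrefuted laboratory abnormality an adverse event on that ground alone; two other definitions disagree, and counts can be inflated more in WATCH than in maintenance

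*Combined protocol and SAP*

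**What the plan says.** Three places define when a laboratory finding is an adverse event (AE).

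- **Section 8.1, Abnormal Laboratory Values:** "A clinical laboratory abnormality will be documented as an adverse event if any one of the following conditions is met". The first condition is "The laboratory abnormality is not otherwise refuted by a repeat test to confirm the abnormality". The other two are that the value points to disease or organ toxicity, or that it needs active management.
- **Section 8.1, Adverse Event:** "Abnormal results of diagnostic procedures are considered to be adverse events if the abnormality" meets one of five qualifiers: withdrawal, association with a serious event, clinical signs or symptoms, further treatment or tests, or that it "is considered by the investigator to be of clinical significance".
- **Section 8.3:** the definition is repeated in the widest terms, "including any abnormal sign, symptom, disease, or abnormal laboratory finding temporally associated with the subject’s participation in the research".

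Two other provisions narrow the field. Under Preexisting Condition in section 8.1, "A preexisting condition will be recorded as an adverse event if the frequency, intensity, or the character of the condition worsens". Section 8.2 groups clearly related findings under one diagnosis.

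Section 7.2 catalogues AEs and serious AEs in the same way as infections, which are tallied by regimen and cohort without statistical comparison. Section 8.5.1 asks the DSMB to review AE frequency and severity in the no-maintenance group against the maintenance group. The visit tables mark laboratory data collection at all 20 post-randomization WATCH visits and at every treatment-group visit; section 6.3.2 puts the latter at 9 to 13.

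**The concern.** A confirmation step normally excludes spurious results before clinical relevance is judged. Here it is written as a sufficient condition: a value not refuted is an AE with no test of severity, change from enrolment or clinical significance. The Adverse Event paragraph would not list the same value, and section 8.3 would. Two coordinators could classify one result differently and both comply.

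The looser the rule, the more the count depends on how often blood is tested, and the two arms are scheduled differently. The AE tally describes the harms of each regimen, goes to the DSMB, and can feed the planning estimates of Aim 5. Part of the rationale for withholding maintenance is to avoid adverse effects (sections 1 and 11). A definition that can add events preferentially to WATCH works against seeing that benefit, and could carry a wrong AE rate into the larger trial.

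**Working it through.** **1. The rule as logic.** Let R = refuted by a repeat, D = suggests disease or organ toxicity, M = requires active management. The laboratory rule is AE = (not R) or D or M. A confirmed value and a never-repeated value both have R false, so both are AEs whatever D and M are. D and M matter only for refuted values.

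| Value | 8.1 laboratory rule | 8.1 Adverse Event qualifiers | 8.3 wording |
|---|---|---|---|
| New, confirmed, no symptoms, no action, judged not significant | AE | none met | AE |
| Same, never repeated | AE | none met | AE |
| Refuted, no action, no suggestion of toxicity | not AE | none met | arguably AE |
| Refuted, but had already led to treatment | AE (M) | AE | AE |

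The first two rows are the conflict. No passage ranks the three texts.

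**2. Scheduled laboratory occasions.** The plan's figure for the treatment group is reproduced with visits = floor(span/interval) + 1, counting Visit 1. Over 96 weeks this gives floor(96/12) + 1 = 9 and floor(96/8) + 1 = 13. (Over 106 weeks, 8-week spacing would give 14; the table stops at Visit 13.) WATCH has weeks 0, 4, 8, 12 and 16 (5 visits), then every 6 weeks from 22 to 106, (106 − 22)/6 + 1 = 15, so 20 in all. The ratio is 20/13 = 1.54 to 20/9 = 2.22.

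Follow-up is 24 months in both arms, so the same ratio applies per person-month: 20/24 = 0.83 occasions against 9/24 = 0.38 to 13/24 = 0.54. A person-time denominator does not remove it.

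**3. Effect on counts, by assumption.** Suppose each visit has the same chance q of a new qualifying value in both arms, with labs drawn at every visit. The documents do not give q. Expected events per patient are nq; the share of patients with at least one is 1 − (1 − q)^n.

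| q | Events at n = 9 / 13 / 20 | Share with at least one |
|---|---|---|
| 0.05 | 0.45 / 0.65 / 1.00 | 37% / 49% / 64% |
| 0.10 | 0.90 / 1.30 / 2.00 | 61% / 75% / 88% |
| 0.30 | 2.70 / 3.90 / 6.00 | 96% / 99% / 99.9% |

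Event counts carry the full ratio of 1.54 to 2.22. The ratio of patients with any event falls from 1.32–1.73 at q = 0.05 to 1.01–1.04 at q = 0.30, but by then almost everyone has an event and the summary no longer separates the arms.

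**4. How far repeats matter.** Assume k = 10 analytes, each out of range by chance with p = 0.05, independently, over v visits (none of this is in the documents).

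- No value is ever repeated and later panels do not count as repeats: kpv = 10.0 in WATCH against 4.5 to 6.5, ratio 1.54 to 2.22.
- The next visit's panel counts as the repeat, and a last-visit abnormality stands because nothing follows it: kp²(v − 1) + kp. WATCH: 0.025 × 19 + 0.5 = 0.98. Maintenance: 0.025 × 8 + 0.5 = 0.70 to 0.025 × 12 + 0.5 = 0.80. Ratio about 1.2 to 1.4.
- As above without the last-visit term: 0.48 against 0.20 to 0.30.

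WATCH is higher each time, but the absolute number of spurious events per patient in WATCH ranges from about 0.5 to 10 according to an unstated repeat practice.

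**The case against.** The strongest reply is that section 8.1 should be read as a whole. An AE must develop or worsen during the study, preexisting conditions count only on worsening, and section 8.2 groups related results. Chance values are the ones a repeat would usually refute. Labs come from routine care, and the WATCH text makes them conditional at Visit 1 and at weeks 22, 46, 70 and 94. The AE summary is descriptive, events are graded and recorded by type, relation to therapy and outcome, and the termination criterion for toxicity in section 8.4 uses Grade 3 serious events. The listed secondary endpoint for harm is infections, which this rule does not touch. The Adverse Event paragraph also says if, not only if, so the contradiction is not strict.

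Much of this stands, and it rules out a stronger reading. A reader might infer that nearly every out-of-range value becomes an AE and that the tally tracks visits rather than harm. The documents do not support that. Stable residual creatinine or anaemia is limited by the preexisting-condition rule, the number of panels actually drawn per arm is unknown, and true drug toxicity could raise the maintenance count. Nor is it shown that spurious values would swamp real toxicity: the large figures in step 4 require that no repeat is ever done.

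The reply does not dispose of the point. The preexisting-condition rule does not reach new trivial values. Grouping needs a diagnosis to group under. The laboratory paragraph is the more specific text, and section 8.3 supports its broad reading. Remote visits in the treatment group (section 6.2) could widen the gap in laboratory occasions. Descriptive estimates are this trial's product, so being descriptive is no protection.

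**Conclusion.** The point holds as a defect of definition with a plausible, unquantified imbalance. Non-refutation alone makes a new, confirmed or never-repeated, clinically trivial value an AE; one other definition is narrower, one is broader, and none is said to govern. Scheduled laboratory occasions favour detection in WATCH by 1.54 to 2.22. If routine labs follow the schedule, event counts of such values can be inflated more in WATCH, distorting the tally by regimen and the AE frequency comparison given to the DSMB.

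The actual distortion cannot be computed without analyte numbers, abnormality rates and repeat frequency. Trivial values would not meet the criteria for a serious event, so the Grade 3 serious-event criterion is largely unaffected. The point merits correction because the edit is small, not because the trial's conclusions depend on it.

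**What to change.** Reconcile the Adverse Event and Abnormal Laboratory Values paragraphs of section 8.1 and the definition in section 8.3 into one rule, and cite it in all three places:

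- A laboratory abnormality is an AE if it is new or worse than at enrolment **and** meets at least one of: study withdrawal; association with a serious AE; clinical signs or symptoms; additional treatment or tests; clinical significance in the investigator's judgement; suggestion of disease or organ toxicity; need for active management.
- Non-refutation by a repeat is not sufficient by itself. An abnormality that a repeat refuted and that led to no action is not an AE. One that had already led to action still is.
- The confirmatory repeat does not by itself count as an additional test; otherwise every repeated value would re-enter.

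In section 7.2, tabulate laboratory-only AEs separately from clinical AEs by regimen and cohort, with the number of laboratory assessments per arm as denominator. Give the DSMB the same split.

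The cost is a few sentences and one table line. Routine results are already entered in the study database, so events can be reclassified and assessments counted. The downside is that isolated, untreated, non-significant values are no longer listed as AEs, though they remain in the laboratory data. The visit imbalance persists for events that still qualify, which is why the denominator is needed.

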### **Hospitalization, Prolonged Hospitalization or Surgery**

Any adverse event that results in hospitalization or prolonged hospitalization will be documented and reported as a serious adverse event unless specifically instructed otherwise in this protocol. Any condition responsible for surgery will be documented as an adverse event if the condition meets the criteria for an adverse event.

Neither the condition, hospitalization, prolonged hospitalization, nor surgery will be reported as an adverse event in the following circumstances:

- Hospitalization or prolonged hospitalization for diagnostic or elective surgical procedures for a preexisting condition. Surgery should **not** be reported as an outcome of an adverse event if the purpose of the surgery was elective or diagnostic and the outcome was uneventful.
- Hospitalization or prolonged hospitalization required to allow efficacy measurement for the study.
- Hospitalization or prolonged hospitalization for therapy of the target disease of the study, unless it is a worsening or increase in frequency of hospital admissions as judged by the clinical investigator.

## **8.2 Recording of Adverse Events**

At each contact with the subject, the investigator will seek information on adverse events by specific questioning and, as appropriate, by examination. Information on all adverse events will be recorded immediately in the source document, and also in the appropriate adverse event module of the case report form (CRF). All clearly related signs, symptoms, and abnormal diagnostic procedure results will be recorded in the source document, though grouped under one diagnosis.

All adverse events occurring during the study period will be recorded. The clinical course of each event will be followed until resolution, stabilization, or until it has been determined that the study treatment or participation is not the cause. Serious adverse events that are still ongoing at the end of the study period will be followed up to determine the final outcome. Any serious adverse event that occurs after the study period and is considered to be possibly related to the study treatment or study participation will be recorded and reported immediately.

## **8.3 Reporting of Serious Adverse Events and Unanticipated Problems**

All adverse events will be reviewed and recorded in “real time” and reviewed systematically every month by the PI. Adverse events are defined as any untoward or unfavorable medical occurrence in a human subject, including any abnormal sign, symptom, disease, or abnormal laboratory finding temporally associated with the subject’s participation in the research, whether or not considered related to the subject’s participation in the research.

Serious Adverse Events (SAE) will be reported immediately within 1 business days to the UNC IRB, and within 5 business days to the FDA according to the requirements of the IND. Reporting will be done electronically to the UNC IRB (as per current standard operating procedure) and by Fax to both institutions.

For reportable deaths, the initial submission to the UNC IRB may be made by contacting the IRB Director or Associate Director. The AE/Unanticipated Problem Form is required as a follow up to the initial submission.

### **Other Reportable events:**

The following events will also be reported to the UNC IRB:

- Any adverse experience that, even without detailed analysis, represents a serious unexpected adverse event that is rare in the absence of drug.
- Any adverse event that would require modifications to the protocol or informed consent form, or would prompt other action by the IRB to assure protection of human subjects.
- Information that indicates a change to the risks or potential benefits of the research, in terms of severity or frequency

- Change in FDA safety labeling or withdrawal from marketing of a drug, device, or biologic used in a research protocol.
- Breach of confidentiality
- Change to the protocol taken without prior IRB review to eliminate apparent immediate hazard to a research subject.
- Incarceration of a subject when the research was not previously approved under Subpart C and the investigator believes it is in the best interest of the subject to remain on the study.
- Complaint of a subject when the complaint indicates unexpected risks or the complaint cannot be resolved by the research team.
- Protocol violation or deviation.

### **8.3.1 Notifying the FDA**

The PI will report certain study events (IND safety reports) in an expedited fashion to the FDA. These written notifications of adverse events are referred to as. The following describes the safety reporting requirements which will be followed by timeline for reporting and associated type of event:

- ***Within 7 calendar days***

Any study event that is:

- associated with the use of the study drug
- unexpected,
- fatal or life-threatening, and

- ***Within 15 calendar days***

Any study event that is:

- associated with the use of the study drug,
- unexpected, and
- serious, but not fatal or life-threatening

-or-

- a previous adverse event that was not initially deemed reportable but is later found to fit the criteria for reporting (reporting within 15 calendar days from when event was deemed reportable).

Any finding from tests in laboratory animals that:

- suggest a significant risk for human subjects including reports of mutagenicity, teratogenicity, or carcinogenicity.

### **Additional reporting requirements**

The PI will also identify in IND safety reports all previous reports concerning similar adverse events and to analyze the significance of the current event in light of the previous reports.

### **Reporting Process**

Adverse events will be submitted on our SAE form (see Appendix D) or in a narrative format, along with FDA form 1571. If supplied as in a narrative format, the minimum information to be supplied is noted above at the beginning of section.

#### **8.4 Stopping Rules**

Trial Termination: It is anticipated that some of the patients will have a relapse even among those treated with maintenance immunosuppression. In a recent large randomized controlled trial of maintenance therapy with rituximab vs azathioprine, 5% of patients in the rituximab-treated group and 29% of those in the azathioprine-treated group had a major relapse over 28 months of follow up (Guillevin L et al *N Engl J Med* 2014;371:1771-80.). Major relapses were defined as involving a major organ or life threatening (e.g. alveolar hemorrhage, glomerulonephritis, mononeuritis with new motor deficits). In addition, minor relapses (e.g. recurrence of epistaxis, arthralgias, or skin rash) occurred with greater frequency (e.g. in the RCT trial of maintenance therapy with rituximab vs azathioprine, minor relapses occurred in 11% vs 16% of patients respectively).

In order to minimize bias in the assessment of the primary endpoint of relapse, this relapse assessment will be done by a physician serving as a reviewer blinded to the patients' identity and treatment arm. [name], Associate Professor of Medicine, Associate Division Chief, Division of Rheumatology, Allergy, and Immunology at UNC will serve as the blinded reviewer for this study. [name] has vast experience and expertise in ANCA vasculitis. [name] will NOT be involved in the care of patients enrolled in this study. Every 3 months, [name] will review all of the available clinical assessments for relapse adjudications based on the BVAS scores, clinical history, review of systems, physical examination and laboratory data. A report form will be generated to provide him with this information while being blinded to the treatment arm (medication list will be omitted). Patients will be treated according to the treating-physician's assessment in the interval between these blinded reviews. [name] assessment will not be used to guide therapy. For the purpose of data analysis, in cases where the assessment of relapse done by [name] differs from the treating physician's assessment, the assessment used for final data analysis will be the blinded reviewer ([name]).

Given the small number of patients in each treatment group in our proposed proof of concept trial (~15 patient per group), it is difficult to decide a priori of a number of relapses in the No-maintenance therapy group that would prompt termination of the trial. We propose prompt consideration of early termination of the trial if the following criteria are met at any point over the course of the trial (provided a sufficient number of patients are accrued and randomized):

- 1)  $\geq 50\%$  major relapse rate in the NO-maintenance therapy group, AND
- 2)  $\geq 40\%$  major severe relapse rate over the maintenance therapy (control) group. Major relapse is defined as involving a major organ or life threatening (e.g. alveolar hemorrhage, glomerulonephritis, mononeuritis with new motor deficits).

The DSMB will be contacted for a review of the study outcomes whenever 2 new relapses have occurred in the NO-maintenance therapy (surveillance) group.

The " $\geq 40\%$  major severe relapse rate over the Maintenance Therapy Group" criterion stems from the small number of patients anticipated in each of the randomized groups ( about 15 per group) and for the recognized potential relapse rate in the control (maintenance immunotherapy) group (in the MAINRITSAN trial, the major relapse rates were 5% and 29% over 28 months for the rituximab and azathioprine groups respectively) (Guillevin L et al *N Engl J Med* 2014;371:1771-80.).

During the conduct of the trial, and before all the patients are accrued, a threshold of 50% relapse rate may be attained with a very small number of events (1-2). The additional  $\geq 40\%$  over the Maintenance Therapy criterion is meant to verify that the study is not terminated prematurely by a chance event.

Conversely, we propose the following criterion to prompt consideration of early termination of the trial for toxicity if there is a  $\geq 40\%$  increase in Grade 3 severe serious adverse event rate in the maintenance therapy (control) group compared to the NO-maintenance therapy group.

